5-24-2021

Pharmacologically-based Strategies for Opioid Substitution Therapy During Pregnancy

PRO18070495 / STUDY19100128

NCT03831113

Protocol version 1.8

The Eunice Kennedy Shriver National Institute of Child Health and Human Development (NICHD)

Principal Investigator:

[name]
Magee-Womens Hospital
[name]
[name]

Specific Aim 4

Specific Aim 4 compares dose reduction strategies for Suboxone or Subutex in pregnancy that are based on the pharmacodynamic and pharmacokinetic characteristics of BUP.

a) Primary Research Questions

1. Is adherence during dose reduction influenced by the magnitude or frequency of a given dose reduction?
2. Is adherence during dose reduction influenced by dosing frequency?
3. Does mu receptor sensitivity change during dose reduction?

b) Eligibility Criteria

Inclusion Criteria – must meet all of the following:

1. On a stable BID, TID or QID dosing regimen of BUP for at least 2 weeks as part of an established medication- assisted treatment (MAT) program.
2. Willingness to undergo supervised dose reduction
3. Subjects on BID, TID or QID dosing, willing to be assigned to the Magnitude, Frequency, or Dosing group, depending on their current dosing
4. Single gestation between 14-30 weeks at the initiation of dose reduction
5. On a BUP dose between 6- 24 mg daily (lower doses will not provide sufficient data points)
6. Willingness to have urine samples tested for drugs of abuse and blood samples tested for BUP+M concentrations during the Medical Supervised Withdrawal (MSW) clinic appointments
7. Willingness to attend weekly or biweekly MSW clinic appointments and to have daily contact via text messaging to complete daily logs of sleep quality, withdrawal symptoms and symptoms of craving. Subjects may consent to receiving daily text messages with a link to a REDCap where they can complete the daily questionnaires electronically. Alternatively, they may complete hard copies of the questionnaires and return them during their weekly clinic visits.
8. Willingness to attend psychosocial support meetings, as needed.

Exclusion criteria – cannot meet any of the following:

1. Current use of cocaine, heroin, benzodiazepines, barbiturates, phencyclidine (PCP), or opioids other than BUP
2. Currently taking more than two mental health medications

3. Active moderately severe depression (PHQ-9 score ≥ 15 or suicidal ideation)
4. Current incarceration

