The pharmacologic properties of BUP that inform this specific aim include a long half-life that suggests that any dose reduction should not occur more often than every 5 days to allow the impact of that dose change to manifest. The long half-life also suggests that a higher reduction (i.e. 2 mg) will be well tolerated as the reduction in drug exposure (i.e. the reduction in plasma concentrations over time) will be gradual over the ensuing 5 days till a new steady state is reached. The third PK and PD characteristic of BUP is that plasma concentrations are better sustained above a specified critical value with more frequent dosing.⁵¹ Based on these pharmacologic characteristics of BUP, we will evaluate three strategies for supervised dose reduction. We will recruit 3 groups of pregnant women who are on a stable dose of BUP and are committed to supervised dose reduction. Recruitment will occur in our Pregnancy Recovery Center (PRC), from offices of other BUP writers, and from the Emergency Department (ED) at Magee. We will also enlist [name], MD at High Risk Obstetrical Consultants, in Knoxville, TN to assist in recruitment of eligible subjects at his institution for Specific Aim 4 only, pending IRB approval. [name] is an expert in dose reduction/detoxification during pregnancy and has published extensively on this topic. [name] will adhere to this multicenter protocol and Data Safety Monitoring Plan and report periodically to [name].

At MWH, pregnant women with an opioid use disorder generally come for initiation of methadone or BUP as part of a MAT program. They often present to the ED and are told to contact the PRC if they wish to start BUP or they are admitted if experiencing withdrawal for transition to methadone. Those who prefer to initiate treatment with Suboxone or Subutex will be targeted for recruitment. [name] is a primary provider at High Risk Obstetrical Consultants for opioid dependent women and we structured our dose reduction strategy based on his experiences.

Consenting subjects will be assessed for depression at the Pre-Study Screening. The Patient Health Questionnaire-2 (PHQ-2) will be administered as a screen for depression. If the PHQ-2 score is 3 or greater, major depressive disorder is likely and subjects will be further evaluated with the Patient Health Questionnaire-9 (PHQ-9). The PHQ-9 is a multipurpose instrument for screening, diagnosing, monitoring and measuring the severity of depression.

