- A PHQ-9 score of ≥ 15 represents moderately severe depression. Subjects with a score of ≥ 15 at the Pre-Study Screening will be excluded from participating in the study and will be referred to a mental health provider.

Note: Question 9 on the PHQ-9 is a single screening question on suicide risk. If a subject answers yes to question 9, they are ineligible to continue with the study and will be immediately referred to a mental health provider for further assessment.

Once recruited subjects are on a stable dose of Suboxone or Subutex for 2 or more weeks, we will initiate one of three dose reduction strategies. We will compare tolerance in the same person to an alternating 1 mg vs 2 mg weekly reduction (Magnitude group, n=10). In a second group (Frequency group, n=10) we will compare tolerance in the same person to an alternating 2 mg reduction occurring weekly vs bi-weekly. All subjects in the Magnitude and Frequency groups will be on TID or QID dosing. In a third group (Dosing Group, n=10) we will compare tolerance to either the Magnitude or Frequency reduction schedule in women who are on a BID dosing regimen. The comparisons in these three groups will address those fundamental questions required for development of a rational dose reduction strategy. Each of these strategies addresses a specific question about maternal accommodation to the specified dose change. The dose reduction magnitude of 1 mg vs 2 mg and the frequency of reduction of weekly vs bi-weekly selected are based in large part on the work of Sigmon et al.⁴⁷ but larger and more frequent reductions could be considered. We chose this modest reduction strategy as we were concerned that more aggressive changes could lead to subject withdrawal and dissatisfaction. In the study of Sigmon et al.⁴⁷, only 50% of participants were opioid abstinent with the 4-week taper (i.e. 1.75 mg per week). We believe a slower taper regimen could improve upon this outcome. Table 1 provides an example of the dose reduction strategy assuming, as an example, a starting dose of 16 mg daily. Subjects on TID or QID dosing will be assigned to either the Frequency or Magnitude groups based on their current dosing. Subjects on BID dosing will be assigned to the Dosing group.

- Subjects assigned to the Frequency group will have dose reductions of 2 mg on alternating intervals of 1 and 2 weeks.
- Subjects assigned to the Magnitude group will have alternating reductions of 1 then 2 mg every week.

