Week 1	16	16	Refer to the appropriate dose schedule in the Frequency or Magnitude columns
Week 2	14	15	
Week 3	14	13	
Week 4	12	12	
Week 5	10	10	
Week 6	10	9	
Week 7	8	7	
Week 8	6	6	
Week 9	6	4	
Week 10	4	3	
Week 11	2	1	
Week 12	2	0	
Week 13	0	0	

e) Statistics

The outcome(s) of interest are the pharmacodynamic endpoints that reflect the acclimatization of the mu receptors and opioid-affected brain functions. Each subject in a group will undergo alternating treatments to minimize any between subject differences that would impact the response to the decrease in dose. In this study, we will rely on scores from the self-administered VAS questionnaires. We will determine both an average and highest value for each of the VAS questionnaires weekly. The average values over the 7 days of

that given dose from the VAS questionnaires will be combined to create a single score for each week. A similar approach will be taken for the highest rather than average values. Based on the study of Dunn et al ^{46,47}, the mean value for the withdrawal VAS questionnaire (scale 1-10) in non-pregnant subjects was 30 with a standard deviation of ~25. These values are estimates since graphs were provided but not tabular data. A difference of 25% in the VAS combined scores between any of the comparisons would seem clinically meaningful. Thus, a sample size of 10 in each group is sufficient to detect a difference in VAS scores between any of the comparison groups. The comparisons in the Frequency group will be VAS scores between the 1 vs 2 week reductions. The comparisons in the Magnitude group would be VAS scores between the 1 and 2 mg reductions. The comparison in the Dose group will be a comparison of the VAS scores during the 1 mg and 2 mg reductions. Also, VAS scores in the Dose group will be compared to the VAS scores in the Magnitude group both at the 1 and 2 mg reductions. The change in mu receptor sensitivity will be determined by comparing the BUP+M

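### The dosing-frequency question compares VAS levels between non-randomised BID and TID/QID women without a designated baseline or any adjustment for one

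*Combined protocol and SAP*

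**What the plan says.** Section a) Primary Research Questions asks: "Is adherence during dose reduction influenced by dosing frequency". For the outcome, section e) Statistics states that "we will rely on scores from the self-administered VAS questionnaires". Daily scores are averaged over the seven days at a dose, and the averages at "that given dose from the VAS questionnaires will be combined to create a single score for each week". The weekly highest values are treated the same way. Both are levels, not changes.

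The only named analysis that contrasts dosing regimens is in section e): "VAS scores in the Dose group will be compared to the VAS scores in the Magnitude group", at both the 1 mg and the 2 mg steps. Section d) Study Design adds that adherence, cravings and sleep will be compared across groups, but gives no method.

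Group membership follows existing treatment. Section d) says "Subjects on BID dosing will be assigned to the Dosing group", and that the Magnitude and Frequency groups consist of women on TID or QID. Under the design no woman is moved from one regimen to another.

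Section e) describes the protection against differences between women: "Each subject in a group will undergo alternating treatments to minimize any between subject differences". Section d) gives a pharmacological reason to expect the regimens to differ: "plasma concentrations are better sustained above a specified critical value with more frequent dosing".

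On timing, the list in section c) Pre-Study Screening contains no VAS, and section d) describes daily VAS during the reduction process. Table 1 shows Week 1 at the unreduced 16 mg example dose.

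**The concern.** The 1 mg versus 2 mg contrast and the 1-week versus 2-week contrast are each made within a woman, so her usual level of symptoms largely cancels. The BID versus TID/QID contrast has no such protection. Each woman contributes to one side only, and her side was fixed by the regimen she was already taking.

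If more frequent dosing sustains concentrations better, as section d) expects, women on BID may report more withdrawal, more craving or poorer sleep while still on their stable dose. A comparison of VAS levels at the 1 mg and 2 mg steps would carry that gap forward in full. The result would then be read as BID dosing making reduction harder to tolerate, even if the reduction itself affected both groups equally. At stake is the interpretation of one of the three primary questions of the aim.

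**Working it through.** **Inputs from the plan (section e) and its sample size table).** One VAS item: mean 30, SD about 25. Anticipated sum over four items: 120 = 4 × 30. Difference called clinically meaningful: 25%, so 0.25 × 120 = 30 points on the sum. Group size: 10. Alpha, sidedness, power and the SD of the sum are not stated. The documents also describe the items as scored 0–10 or 1–10, which does not fit a mean of 30; the figures below use the scale implied by 30 and 120.

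**Step 1: the plan's own table.** A two-sample t calculation on raw scores with SD 25, one-sided alpha 0.05, 80% power and differences of 18, 24, 30 and 36 points gives 25, 15, 10 and 7 per group. This matches the plan's table exactly. Alpha, sidedness and power are assumptions, and some paired calculations come close (for example a paired z-test, two-sided 0.05, 95% power: 26, 15, 10, 7). The match therefore does not prove which method was used, but it needs no baseline term.

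**Step 2: SD of the sum.** SD 25 is the value that reproduces the table. If the four items were uncorrelated, each with SD 25, the SD of the sum would be √4 × 25 = 50. Both are carried forward.

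**Step 3: effect of a prior gap.** Suppose reduction affects both groups equally, but BID and TID/QID women already differed by a gap g on the summed score. The documents give no value for g, so 10, 20 and 30 are assumed. Each woman contributes one score per step size.

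- SE = SD × √(1/10 + 1/10): 11.18 at SD 25 and 22.36 at SD 50.
- Two-sided test at 0.05 on 18 degrees of freedom, critical value 2.101, noncentrality g/SE.

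| Assumed prior gap | g/SE, SD 25 | P(significant), SD 25 | g/SE, SD 50 | P(significant), SD 50 |
|---|---|---|---|---|
| 10 | 0.89 | 13.5% | 0.45 | 7.1% |
| 20 | 1.79 | 39.5% | 0.89 | 13.5% |
| 30 | 2.68 | 71.8% | 1.34 | 24.6% |

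The nominal rate is 5%. The bias in the estimated difference is g itself, whatever the SD; the SD only decides how often the test flags it. At g = 30 the probabilities equal the power for a true 30-point effect, so the raw comparison cannot distinguish the two.

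**Step 4: what adjustment does to precision.** With ANCOVA, n per group = 2 × [SD × √(1 − ρ²) × (1.96 + 0.84)/30]², two-sided 0.05 and 80% power. The correlation ρ between the Week 1 score and the on-reduction score is not in the documents, so a range is shown.

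| ρ | SD 25 | SD 50 |
|---|---|---|
| unadjusted | 11 | 44 |
| 0.3 | 10 | 40 |
| 0.5 | 9 | 33 |
| 0.7 | 6 | 23 |
| 0.8 | 4 | 16 |

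These normal-approximation figures ignore the lost degree of freedom, but they show that adjustment need not cost precision and may gain some.

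**The case against.** Four points can be made for the plan.

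*A pre-reduction VAS may well be collected.* Section d) starts women on a schedule like Table 1 with daily VAS, Table 1 begins with a week at the start dose, and section e) forms a score for each week. This stands. A reader might infer from the screening list that no pre-reduction VAS exists, but the documents do not support that. The gap is that the plan neither says Week 1 is scored nor designates it as baseline.

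*The unadjusted comparison is informative.* If BID dosing produces more symptoms on a stable dose, those symptoms may be part of the effect of dosing frequency and may bear on adherence. Adjusting for Week 1 removes that part. This also stands. A reader might conclude that the planned comparison cannot answer question 2, but that goes too far: it answers a question about symptom level during reduction, mixed with prior state. That is why both contrasts should be shown.

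*Chance imbalance between two groups of 10 is not a defect.* A test's standard error already allows for it. With both groups drawn from one population, a gap of 30 points or more on the sum has probability of about 0.7% at SD 25 and 18% at SD 50 (normal approximation). The concern is a systematic gap between regimens.

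*Adjustment does not make the groups comparable.* Whatever else led a woman to BID rather than TID or QID remains. This stands and limits what may be claimed even after the fix.

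**Conclusion.** The concern holds in a limited form. The only named test of dosing frequency compares VAS levels between different, non-randomised women, with no designated baseline and no adjustment. The alternating design does not protect it, and the protocol supplies its own reason to expect a prior difference. As written, the comparison does not separate tolerance of reduction from symptoms already present.

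The size depends on a gap that the documents do not give. With assumed prior gaps of 20 or 30 points and equal tolerance, the raw test would be significant about 40% or 72% of the time at SD 25, and 14% or 25% at SD 50. These figures assume 10 women per group, one score per woman and a two-sided 5% t-test. They show what a gap would do, not that one exists. The improvement is worth making because it is cheap and because a baseline not recorded before the first reduction cannot be recovered later.

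**What to change.** 1. In section d), state that all four daily VAS are completed during Week 1 of Table 1, at the start dose and before the first reduction.
2. In section e), designate the Week 1 combined score as baseline, formed as the later weekly scores are (average with average, highest with highest).
3. Analyse Dose versus Magnitude at the 1 mg and 2 mg steps by ANCOVA adjusted for the Week 1 score. Fix this method in advance, since ANCOVA and change from baseline can disagree when non-randomised groups start at different levels. Show the unadjusted level comparison alongside.
4. Describe the result as a non-randomised comparison in which other confounding by regimen remains.

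The cost is seven days of a questionnaire already in use, in a week already on the schedule, and one degree of freedom. That matters somewhat more if fewer than 10 BID women contribute. Table 1 lets the Dosing group follow the Frequency schedule, which has no 1 mg steps; with an assumed 5 BID women against 10, raw power for 30 points falls from 72% to 53% at SD 25, and from 25% to 17% at SD 50. The adjusted contrast also leaves out any dosing-frequency effect already present on the stable dose, and the report should say so. No dose or reduction schedule changes.

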- Subjects in the BID group will be assigned to the Dosing group. The Dosing group may follow the Magnitude (alternating 1 mg and 2 mg dose reductions weekly) or Frequency (2 mg dose reductions on alternating intervals of 1 and 2 weeks) dose reduction schedules.

In all groups, the alternating approach will continue until the subject is Suboxone or Subutex free or at the lowest dose tolerable. We appreciate that some subjects may not tolerate the recommended dose reduction especially at the lower doses. Subjects that experience withdrawal symptoms may be treated with ancillary medications such as Benadryl or clonidine. To minimize any risk of relapse, subjects who are intolerant to a given reduction will be allowed to go back to the last tolerated dose taken prior to the reduction. Visual Analog Scale (VAS) scoring will document their intolerance and this, combined with pharmacological data from the subject, will inform our development of an optimized pharmacological approach to dose reductions. After the subject has been on the higher dose for one week we will re-initiate the dose reduction strategy to which she was assigned. We will repeat this process one more time and if she remains intolerant to further dose reductions, we will not attempt further reductions but rather will maintain her on her current dose. If the subjects desires additional attempts at dose reduction, we will accommodate her request. At this time, she may elect to re-initiate the original dose reduction strategy or select an alternative reduction strategy. For all subjects, we will continue the surveillance approach we have in place throughout the pregnancy, delivery, and into the postpartum period.

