In all 3 groups, daily adherence, cravings and sleep measures will be compared within and across groups. During the Pre-Study Screening, we will explain the study to the subject and ask that she completes an Intake Questionnaire to better understand any previous experiences she may have had with opioid treatment or detox programs. We will also perform urine and blood testing to assure all entry criteria are fulfilled. Once consent is obtained, we will initiate a Suboxone or Subutex dose reduction schedule similar to the one shown in Table 1. To ascertain the impact of a dose change, all subjects will complete 4 daily VAS questionnaires similar to those used by Dunn et al. ⁴⁶ to assess withdrawal, cravings, sleep duration and sleep quality. The scales will range from a score of 0-10 for each question. Subjects that wish to be contacted via text will be sent a daily text with a link to the REDCap website where they can complete the VAS

questionnaire electronically throughout the dose reduction process. Subjects that are unable to receive daily text messages will be provided hard copies of the VAS questionnaire and instructed to return the completed forms to research staff at their next appointment. Clinic visits will occur weekly or biweekly at which time we will monitor plasma BUP+M, neurotransmitter and cotinine concentrations and perform a comprehensive urinary toxicology test. Additionally, at each clinic visit we will administer the Weekly Follow-up and Weekly Smoking and Alcohol Use questionnaires. We will also collect any completed VAS forms, if applicable, and perform COWS and Subjective Opioid Withdrawal Scale (SOWS) scores to assess current clinical and subjective symptoms of withdrawal and satiety. All subjects will receive psychosocial support, as needed. The timing of the subject's scheduled visits will be determined by their healthcare provider.

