Since our focus is to assess whether the magnitude of the dose change, frequency of dose change and dosing frequency impact adherence during reduction, this pharmacodynamic study will be completed when the subjects are off BUP entirely or on the lowest tolerable dose. However, we will continue to see the subjects weekly or biweekly, monitor their adherence and continue to provide counseling sessions, as needed, until the 6-week postpartum visit. We will also evaluate peripheral blood mononuclear cells (PBMCs) as a surrogate marker of metabolic enzymes and transporters. The expression of drug metabolizing enzymes and transporters in the PBMCs will be correlated with the plasma concentrations of BUP and its major metabolites. Two maternal blood samples will be drawn for PBMC analysis; one during pregnancy and one in postpartum. The first sample will be drawn during the Pre-Study Screening; however, if this is not possible, it may be drawn at any time during pregnancy. The second sample will be drawn at 4-6 weeks postpartum, but as close as possible to the 6-week postpartum visit.

For subjects not enrolled in specific aim 3a or 3b, we will collect a cord blood sample at the time of delivery as well as maternal and newborn hair within 3 days of delivery, when possible. An additional cord blood sample (10 mL) will be drawn for genetic studies related to metabolizing enzymes, if the mother consents. The minimal amount of hair needed is 20 mg but we will ask for 100 mg which is still a very small amount. Hair will be removed from the mothers and baby's head (if consent is granted). Mother will decide where the hair will

be removed from her and her baby. The collection of these samples will be described in full detail during the consent process.

Note: Subjects that consent to participate in specific aims 3 (Parts 1 or 2) will already have the cord blood and hair samples collected as part of that specific aim. The collection of these biological samples only applies to those subjects not already enrolled in specific aim 3.

Table 1.

Dose Reduction Schedules if Start Dose is 16 mg Daily			
Group	Frequency	Magnitude	Dosing
Strategy	Reduce dose by 2 mg weekly then biweekly, repeat till dose=0 or at the lowest possible dose	Reduce dose by 1 and then 2 mg weekly, repeat above till dose=0 or at the lowest possible dose	May elect either the Frequency or Magnitude dose reduction schedule.
Dosing Frequency	QID or TID	QID or TID	BID
Dose			

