concentration each week to the subjects VAS scores on craving and withdrawal symptoms. In women who supplement their weekly BUP regimen with other opioids detected at the weekly clinic visits their VAS questionnaires on withdrawal and craving will be scored as 100. Assay Methods: BUP+M will be assayed using UPLC-MS-MS. We have developed and validated this assay and with the new TQS system the LOQ is 15 ng/ml in plasma. BUP in hair and other tissues will be measured by modification of this method and incorporating elements of methods reported in the literature ^{30,31,33}. Cotinine will be measured by minor modification of the published method ⁵⁵.

Anticipated sum of mean VAS scores	Percent Reduction in VAS scores	Sample Size
120	0.15	25
120	0.20	15
120	0.25	10
120	0.30	7

D. Study Procedures

D.1 Screening for Eligibility

The inclusion/exclusion criteria will be reviewed with the patient's chart. Any woman who appears to be eligible will be informed about the study. If a patient appears to meet the criteria for enrollment and expresses interest in the study, she will be told about the study and asked to sign the informed consent form. She will be asked to sign a medical records

release so that the medical records may be obtained. A copy of the signed consent form will be provided to the patient.

D.1.i. Gestational Age Determination

We will use the criteria recommended by the American Congress of Obstetricians and Gynecologists (ACOG).

D.2 Informed Consent Procedures and Documentation

Written informed consent will be obtained before entry into the trial. Full disclosure of the nature and potential risks of participating in the trial will be made. Women who are not fluent in English will be enrolled by a person fluent in their language and both verbal and written informed consent obtained in that language; if such are not available, they will not be included.

D.3 Specimen Collection

Per standard research procedures for Labor and Delivery samples, Magee Womens Hospital employs staff as part of the Obstetric Specimen Procurement Unit (OSPU), which is responsible for the collection of research study samples on the Labor and Delivery unit. Labor and Delivery samples will only be collected if possible. There is a 3-day window for collection of hair samples. Maternal and infant samples will be collected as shown in Table 2.

D.4 Specimen Analysis and Collection of Negative Control Samples

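### The only analysis stated for primary question 3 has no contrast over time, so as written it does not separate a change in mu receptor sensitivity from falling dose or elapsed time

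*Combined protocol and SAP*

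**What the plan says.** Section a) Primary Research Questions lists three questions. The third is "Does mu receptor sensitivity change during dose reduction". Its analysis is one sentence in section e) Statistics: "The change in mu receptor sensitivity will be determined by comparing the BUP+M", continuing "concentration each week to the subjects VAS scores on craving and withdrawal symptoms". No model, time term, definition of sensitivity or sample size accompanies it.

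Four other statements bear on that sentence.

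- **Dose path.** Table 1 gives the Magnitude strategy as "Reduce dose by 1 and then 2 mg weekly, repeat above till dose=0 or at the lowest possible dose" and the Frequency strategy as "Reduce dose by 2 mg weekly then biweekly, repeat till dose=0 or at the lowest possible dose". Neither column ever rises. The exception, in section d) Study Design, is that "subjects who are intolerant to a given reduction will be allowed to go back to the last tolerated dose taken prior to the reduction", for one week before the taper restarts.
- **Draw time.** Section d) has plasma drawn at weekly or biweekly clinic visits, and the timing of a woman's "scheduled visits will be determined by their healthcare provider". It gives no interval from last dose to draw, nor a day after the reduction. The same section expects exposure to drift down over about 5 days after each step.
- **Score of 100.** Under section e), if other opioids are detected at a weekly visit, "their VAS questionnaires on withdrawal and craving will be scored as 100". Section d) sets each scale at 0-10.
- **Removal.** Under section G. Subject Removal Criteria, a woman whose urine shows other opioids at any time during the study leaves it and another subject takes her place.

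**The concern.** A change in sensitivity means that the same concentration goes with a different level of craving or withdrawal later in the taper than earlier. Setting concentration beside VAS week by week shows whether the two move together. They would do so with constant sensitivity, with changing sensitivity, or if symptoms simply drifted with time while the dose fell on schedule. The stated comparison does not say which contrast would tell these apart.

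Two further features could distort any contrast added later. A plasma sample taken at an unknown time after the dose measures exposure with error, and the size of that error depends on whether the woman doses two, three or four times a day. A value of 100 assigned because another opioid was found is not a measured response to buprenorphine. At stake is one of three primary questions.

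**Working it through.** The plan states no figure for question 3. Its sample-size table (25, 15, 10, 7) can be reproduced with a summed VAS of 120, SD 25, a two-sample t test, one-sided alpha 0.05 and 80% power. Alpha, sidedness and power are inferred. That supports the VAS comparisons only, not this question.

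**1. Dose against week, Table 1, weeks 1-13.** r = Sxy / √(Sxx·Syy), variance inflation = 1/(1 − r²).

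- Magnitude (16, 15, 13, 12, 10, 9, 7, 6, 4, 3, 1, 0, 0): −261/√(377.08 × 182) = −0.996; inflation 135.
- Frequency (16, 14, 14, 12, 10, 10, 8, 6, 6, 4, 2, 2, 0): −240/√(320 × 182) = −0.994; inflation 91.
- With one or two assumed step-backs: r from −0.97 to −0.99, inflation 16 to 40.

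**2. What a plain comparison shows.** Simulation of 400 trials on the Magnitude schedule, 10 women, 13 weekly points. Assumed: concentration proportional to dose, VAS 0-100, within- and between-woman SD 15. Mean concentration-VAS correlation:

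| Truth | Mean r |
|---|---|
| Constant sensitivity | −0.68 |
| Sensitivity rises 50% | −0.68 |
| VAS depends on week only | −0.64 |

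**3. Draw time.** Peak/trough = 2^(dosing interval/half-life). Reading the plan's 5 days to steady state as five half-lives (24 h, assumed), the ratio is 2^(12/24) = 1.41 for BID, 2^(8/24) = 1.26 for TID and 2^(6/24) = 1.19 for QID. Reading it as three half-lives (120/3 = 40 h) gives 1.23, 1.15 and 1.11. In the simulation of step 2, with constant sensitivity and draw-time error of log-SD 0.3 to 0.6 (assumed), an early-versus-late slope test declared a change in 37-47% of trials (Magnitude) or 32-36% (Frequency), against 6-7% without the error. In a separate simulation with untimed BID draws, a constant-sensitivity taper looked changed in 25-64% of trials. Adjusting for hours since dose brought this back to 6-7%.

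**4. Scores of 100, if they are used.** Scoring 10% of weeks as 100 weakened the constant-sensitivity correlation from −0.68 to −0.46. One such week in 13 moves a woman with mean 30 to 30 + 70/13 = 35.4. On the 0-10 scale, 100 is ten times the maximum. The plan's anticipated sum of 120 equals 4 × 30, which fits a 0-100 scale, so the text is using two scales.

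**5. Does a concentration-by-week interaction settle it?** Not on these checks.

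- Linear model, 10 women, timed draws, no 100s: power for a 50% rise is about 0.36 (Magnitude) or 0.32 (Frequency). With 10% of weeks at 100 it falls to about 0.08 or 0.07.
- Taking logs of the non-zero doses lowers the correlation with week only to −0.92 (Magnitude) and −0.95 (Frequency).
- Log response, 30 women on the Magnitude taper, residual SD 6, VAS = −k·ln(dose) with k = 5 to 10 (assumed): power for a halving of sensitivity is 7-9%. With 10% concentration error, constant sensitivity is declared changed in 20-65% of trials.

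**The case against.** The strongest reply is that comparing is an undefined word, and a weekly concentration-response comparison could be examined over time. Frequency plateaus, step-backs and the screening BUP+M sample leave some separation between dose and time. This stands in part: the defect lies in the analysis as described. A reader might infer that the data could never answer question 3, but the documents do not support that.

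Three other strong readings also go too far.

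- A reader might infer that draws are known to be untimed. The text available is silent, and section D.3 refers to a Table 2 of sample collection that is not in that text. The sentence on visit timing concerns who schedules visits, not whether dose time is recorded.
- A reader might infer that scores of 100 will certainly enter this analysis. They do so only if the rule in section e) applies rather than removal under section G.
- A reader might set the 19-41% peak-trough swing against a 1-2 mg step from 16 mg (1/16 = 6.25% to 2/16 = 12.5%) and conclude that draw time swamps the signal. Those are the smallest relative steps in Table 1: 4 to 3 mg is 25% and 3 to 1 mg is 67%. Question 3 also spans the whole taper.

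It is also fair to say that the obvious remedy meets the same difficulty. An interaction model inherits the near-collinearity of dose and week, and its error rates depend on the assumed response shape.

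**Conclusion.** The point holds in this form: as written, the only analysis for primary question 3 contains no contrast over time and does not separate a change in sensitivity from falling dose or elapsed time. The dose-week correlation of about −0.99 comes directly from Table 1. The equal correlations of −0.68 and all error rates rest on assumed slopes, SDs and response shapes, with Monte Carlo error of at most about 2.5 points in the 400-trial runs. Missing draw timing is an absence in the available text. The conflict between scoring 100 and removal, and between 100 and a 0-10 scale, is on the page. This should be corrected, but a better model would not give a definitive answer at this sample size: a reader might infer that an interaction term tests question 3, and the checks in step 5 do not support that.

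**What to change.** 1. At each plasma draw, record the time of the last dose and the day since the last reduction. Adjust the concentration-response analysis for hours since dose.
2. In that analysis use only measured VAS values and leave out any scored as 100. Count and report the weeks left out, since they may mark relapse. Reconcile the scoring rule in section e) with the removal rule in section G, and state one VAS scale throughout.
3. In section e), define the change in sensitivity as a change over time in the concentration-VAS relation, estimated within woman with a confidence interval and reported as exploratory. A concentration-by-week interaction is one such estimate. State that it is nearly collinear with the taper, has low power, and can be biased by concentration error and by the assumed response shape. If log concentration is used, give a rule for values at zero or below the assay limit.

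The cost is small: one or two fields at the draw, revised wording, some lost weeks and an imprecise estimate. Dose times not recorded at the draw may not be recoverable later.
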